### Outcome measures related to the correlation between transmission assays:

The association between DMFA and DSF will be analysed across common timepoints for the two outcomes: (1) whether or not an individual is infectious and (2) the proportion of infected mosquitoes. A mixed effects logistic regression with logit-link will be used to express the association for (1) using the risk ratio. For (2) a mixed effects linear model will be used and the association will be expressed in terms of the slope. We use individual-specific random intercepts in both models to account for the within-individual correlation.

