## Sample size

The sample size is standard for the safety cohorts without formal sample size estimation. Sample size is informed by the anticipated efficacy from an earlier Phase I study and the transmission blocking effects observed in similar Malian cohorts when treated with transmission blocking drugs; this is done for the efficacy cohort only. This sample size for the efficacy cohort (n=30 per group) will give us 97% empirical power to detect >80% reduction in infectivity (defined as the percentage of mosquitoes with at least one oocyst) with a one-tailed test with a 0.025 level of significance when dissecting at least 40 mosquitos per participant at each timepoint. This power calculation is based on an online tool based on mixed effects logistic regression, an expected reduction in infectivity of 90%, an expected baseline proportion of infectivity of 15% for the average participant (accounting for non-infectious participants), and a conservative expected intra-cluster correlation of 0.5. Of note, this includes non-infectious individuals. In the four years that we performed NECTAR studies with a highly similar

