study population, 66.0-79.5% of individuals infected at least one mosquito at enrolment with 14.2-17.0% of mosquitoes becoming infected. The power calculation given above includes all individuals (infectious and non-infectious). If we retain 30 individuals per arm and exclude those individuals who are not infectious at baseline ( $\leq 10$ ), the expected percentage of infected mosquitoes will increase from 15% (in the situation where some individuals infect no mosquitoes) to  $\sim 20\%$ . Based on a mixed effects logistic regression we looked at 200 simulations with an expected reduction in infectivity of 90%, an expected baseline proportion of infectivity of 20% for the average participant, and an expected intra-cluster correlation of 0.4. We estimated 91.5% empirical power to detect  $>80\%$  reduction in infectivity with a one-tailed test with a 0.025 level of significance when including 30 participants (of whom 20 are included in the analysis, i.e. after excluding non-infectious individuals) and dissecting 40 mosquitoes per participant at each timepoint. Importantly, these analyses are based on DMFA where venous blood is offered to mosquitoes. We and others have previously demonstrated that mosquito infection rates are at least 2-fold higher when allowing mosquitoes to feed directly on the skin of participants. When the expected baseline proportion infected mosquitoes is updated to account for higher infection rates by skin feeding (30% for the average participant) and we conservatively increase intra-cluster correlation to 0.8, we estimated 96% empirical power to detect  $>80\%$  reduction in infectivity with a one-tailed test with a 0.025 level of significance when including 30 participants and dissecting 40 mosquitoes per participant.

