**Efficacy outcome measures related to participant infectivity:**

17. Participant infection prevalence, assessed by DSF as the proportion of individuals infectious to any number of mosquitoes, compared within groups between baseline and all feeding timepoints, and between groups at all feeding timepoints (timeframe: day 0 [baseline], 1, and 5)

18. Participant infection prevalence, assessed by DMFA as the proportion of individuals infectious to any number of mosquitoes, compared within groups between baseline and all feeding timepoints, and between groups at all feeding timepoints (timeframe: day 0 [baseline], 1, 5, and 14)

19. The association between naturally acquired anti-gametocyte immune responses and naturally acquired functional TRA on participant infectivity.

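### The DMFA–DSF association is to be reported as a risk ratio, but the planned logit-link mixed model gives an odds ratio and no conversion is stated

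*SAP*

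**What the plan says.** The SAP section *Outcome measures related to the correlation between transmission assays*, under *Analyses in relation to endpoints*, relates DMFA to DSF over their common timepoints for two outcomes: "1) whether or not an individual is infectious and (2) the proportion of infected mosquitoes". For the first it states: "A mixed effects logistic regression with logit-link will be used to express the association for (1) using the risk ratio". It adds: "We use individual-specific random intercepts in both models to account for the within-individual correlation". The second outcome gets a linear mixed model and a slope, and is not in question here.

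Three other places in the SAP bear on this sentence:

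- *Participant infectivity* (same part of the SAP) models the same binary outcome, infectious or not, by logistic regression and reports odds ratios.
- *Mosquito infection prevalence* also pairs a mixed logistic model with odds ratios.
- *Within-group % reduction in proportion infected mosquitoes* wants a relative reduction and specifies a log link.

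The only participant-level infectiousness rate in the SAP is in *Sample size*, for earlier cohorts with a highly similar population: "66.0-79.5% of individuals infected at least one mosquito at enrolment".

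**The concern.** A logit-link coefficient, once exponentiated, is a ratio of odds. With a random intercept it is the odds ratio for a given participant, not averaged over participants. A risk ratio needs either a different link or a further calculation from the fitted probabilities. The sentence names the logit model and the risk ratio with nothing between them, so model and effect measure do not match as written.

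The two measures nearly coincide when the outcome is rare. Here it is common at day 0, which is one of the common timepoints. If the model's direct output were reported under the name the SAP gives it, a positive association between the assays would look stronger than it is.

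**Working it through.** **Plan's own figure.** None. The SAP states no odds ratio, risk ratio, sample size or power for this association, so there is nothing to reproduce.

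**Inputs from the SAP**

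- Infectious at enrolment: 66.0% to 79.5% (*Sample size*). The section says of its calculations that "these analyses are based on DMFA where venous blood is offered to mosquitoes", so this rate is taken as a DMFA rate.
- Common timepoints: DSF is done on days 0, 1 and 5, and DMFA on days 0, 1, 5 and 14. Days 0, 1 and 5 are therefore shared.
- Post-treatment: *Sample size* expects a 90% reduction in infectivity, and 60 of the 90 Cohort 2 participants receive TB31F (Table 3).
- Intra-cluster correlation (ICC): "a conservative expected intra-cluster correlation of 0.5", given for the mosquito-level power model.

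**Not in the SAP, so assumed.** Let p1 and p0 be the probability of being infectious in one assay given a positive or a negative result in the other. These are varied below.

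**Formula.** RR = p1/p0 and OR = [p1/(1−p1)]/[p0/(1−p0)], so OR/RR = (1−p0)/(1−p1).

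**Step 1: both assays at the enrolment rate q.** The margin forces p1 = [q − (1−q)·p0]/q. For q = 0.66 and p0 = 0.4, p1 = (0.66 − 0.136)/0.66 = 0.794 and OR/RR = 0.6/0.206 = 2.9.

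| q | p0 | p1 | RR | OR | OR/RR |
|---|---|---|---|---|---|
| 0.66 | 0.6 | 0.691 | 1.15 | 1.49 | 1.3 |
| 0.66 | 0.4 | 0.794 | 1.98 | 5.78 | 2.9 |
| 0.66 | 0.2 | 0.897 | 4.48 | 34.8 | 7.8 |
| 0.795 | 0.6 | 0.845 | 1.41 | 3.64 | 2.6 |
| 0.795 | 0.4 | 0.897 | 2.24 | 13.0 | 5.8 |
| 0.795 | 0.2 | 0.948 | 4.74 | 73.6 | 15.5 |

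**Step 2: assumed low post-treatment rates.** For 0.30 v 0.10, RR is 3.00 and OR 3.86 (1.3 times). For 0.20 v 0.05, RR is 4.00 and OR 4.75 (1.2 times).

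**Step 3: the random intercept.** The intercept variance is set to ICC/(1−ICC) × π²/3, and the conditional odds ratio that reproduces given marginal probabilities is found by numerical integration. This takes the intercept as independent of the predictor assay, as the model itself does. It also borrows the mosquito-level ICC of 0.5 for a participant-level outcome.

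| p1 v p0 | RR | Marginal OR | Conditional OR | Conditional OR/RR |
|---|---|---|---|---|
| 0.795 v 0.66 | 1.20 | 2.00 | 2.81 | 2.3 |
| 0.90 v 0.40 | 2.25 | 13.5 | 47.9 | 21 |
| 0.30 v 0.10 | 3.00 | 3.86 | 6.88 | 2.3 |

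**Step 4: direction.** A marginal odds ratio is the same whichever assay is the outcome; a risk ratio generally is not. Take an assumed table with DMFA positive in 70%, DSF in 85%, both in 65% and neither in 10%.

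- DSF given DMFA: (0.65/0.70)/(0.20/0.30) = 1.39
- DMFA given DSF: (0.65/0.85)/(0.05/0.15) = 2.29
- OR: (0.65 × 0.10)/(0.05 × 0.20) = 6.5

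One table thus yields three candidate figures, and the SAP does not say which assay is the outcome.

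**The case against.** The strongest reply is that a logistic model can supply a risk ratio, by averaging its predicted probabilities with each assay result imposed in turn. The SAP already uses its logistic models to estimate proportions and keeps odds ratios and log-link ratios apart elsewhere. The sentence may therefore omit a post-estimation step, or contain a slip in the link or in the measure. This stands in part. A reader might infer that an odds ratio will certainly be published as a risk ratio, and the text does not establish that. What remains is that neither the step nor its confidence interval is specified, so the sentence does not fix the estimate.

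A reader might also infer that the odds ratio must be many times the risk ratio at these infectiousness rates. The documents do not support that. The 66.0–79.5% is a single margin from earlier cohorts, and a margin alone does not determine OR/RR. Two of the three common timepoints also follow treatment, when lower rates are expected in the TB31F arms.

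Finally, a reader might suppose that this result decides whether membrane feeding can replace skin feeding. The SAP ties no such decision to it. It lists the relationship between SMFA, DSF and DMFA as an exploratory objective, and the slope for the proportion of infected mosquitoes does not depend on the logit model.

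**Conclusion.** The point holds as a mismatch between the stated model and the stated measure, with no conversion given. The direction is certain: for any positive association the marginal odds ratio exceeds the risk ratio.

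The size is conditional on assumed agreement between the assays. With both at the enrolment rates, the marginal factor is about 1.3–2.6 for weak agreement (p0 = 0.6), 2.9–5.8 at p0 = 0.4 and 7.8–15.5 for strong agreement (p0 = 0.2). At assumed post-treatment rates of 20–30% v 5–10% it is about 1.2–1.3. A random intercept independent of the predictor widens each of these. An analysis pooled over days 0, 1 and 5 mixes these situations.

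The consequence is confined to one of two measures for outcome 24. The primary efficacy endpoint, the day 5 reduction by DMFA, uses a separate log-link model and is not touched.

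**What to change.** Amend the one sentence in *Outcome measures related to the correlation between transmission assays* in one of two ways:

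- **Report an odds ratio**, described as conditional on the participant, in line with the other logistic analyses in the SAP.
- **Keep the risk ratio and say how it is obtained.** One route is to standardise predicted probabilities from the logistic model, averaged over the random-intercept distribution, with a participant-level bootstrap confidence interval. The other is a log-link (modified Poisson) GEE with robust standard errors clustered by participant. Either route must name which assay is the outcome and which the predictor.

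The cost is a sentence or two in the SAP and a few lines of code. It needs no new data and no change to the sample size.

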### Outcome measures related to estimated inhibitory concentrations:

Transmission blocking activity (TBA, the reduction in the proportion of infected mosquitoes) and transmission reducing activity (TRA, the reduction in oocyst numbers/infection intensity) will be determined for DMFA and DSF separately. Baseline infection prevalence and intensity estimates will be used to calculate relative reductions in these transmission measures during follow-up. For SMFA experiments, TRA will be quantified as the relative reduction in oocyst intensity for test samples (one feeder per test sample) compared to pooled naïve serum controls (two feeders). Samples may be tested in one or two independent SMFA experiments.

TRA values for each participant and time-point will be estimated using mixed effect negative binomial regression models with random intercepts for each experiment to account for between experiments differences in oocyst intensity that is achieved in control experiments (SMFA) or baseline measurements (DMFA/DSF).

TBA values for each participant and time-point will be estimated using mixed effect logistic regression models with random intercepts for each experiment to account for between experiments differences in oocyst prevalence that is achieved in control experiments (SMFA) or baseline measurements (DMFA/DSF). Of note: for SMFA TBA estimates are deemed to be less informative than TRA estimates due to the design of these experiments that aim for high oocyst prevalence and density in control experiments.

TRA and TBA estimates will be correlated with TB31F antibody measures to obtain the best possible fit for DMFA, DSF and SMFA separately. This will allow us to estimate IC50 and IC80 values for TB31F for each assay separately and model TRA and TBA estimates based on antibody concentration. TRA/TBA modeling is relevant because the precision of these estimates decreases with decreasing activity. Samples with lower levels of TRA (typically below 80%) and TBA may thus have relatively imprecise estimates. For some analyses, we may thus use TRA or TBA estimates that are inferred from antibody concentration based on the best fit model for the association between antibody concentration and TRA or TBA. For this fit, will use mixed effects models, similar to methods described by Miura et al. and Ramjith et al, adjusting TB31F antibody concentrations measured in serum to reflect whole blood concentrations. These models will estimate Inhibitory Concentration values (e.g. IC80, IC50) based on the best fit.

TB31F concentration in serum at which 80% TRA is expected (IC80) is calculated through (mixed-effects) linear regression by regressing the square root of serum concentration on the log-mean

oocyst ratio, i.e.  $IC_{80} = \left( \frac{\left( \log\left(\frac{100}{100-80}\right) - \hat{\beta}_0 \right)}{\hat{\beta}_1} \right)^2$  where  $\hat{\beta}_0$  and  $\hat{\beta}_1$  are the estimated regression coefficients

for the intercept and slope of the linear model respectively. The delta method will be used to estimate the standard error for the IC80 value and thus a 95% confidence intervals for the IC80 can be calculated. To compare assays (SMFA/DMFA/DSF) we can include a categorical variable in the model as an interaction variable to allow different slopes ( $\hat{\beta}_1$ ) to be estimated for the different assays.

Thereafter comparisons can be drawn for the IC80 values between assays. A similar calculation is made for IC50 values.

Modeled TRA and TBA estimates (based on antibody concentration) will be plotted against observed estimates and may be used to determine the duration of TB31F activity at time-points when no feeding assays were performed. This will be achieved by analysing pharmacokinetic and pharmacodynamic data by means of non-linear mixed effects modeling. We will fit single and multicompartmental methods to the obtained pharmacokinetic data and investigate both linear and non-linear elimination and disposition. Thereafter, we will investigate whether the pharmacokinetics relate with TBA/TRA. The developed pharmacokinetic-pharmacodynamic model will be used for *in silico* exploration of:

- TB31F dosing regimens needed to achieve at least 80% TRA during an epidemiological relevant time frame (e.g. a typical transmission season of three months)
- the effect of monoclonal antibody engineering, resulting in a longer circulation half-life due to a more favorable pH-dependent binding to human neonatal receptor, on the dose needed to achieve at least 80% TRA during an epidemiological relevant time frame (e.g. a typical transmission season of three months)

We may calculate the percentage of individuals per group that have at least 50%, 80% and 90% TRA per timepoint and per study arm and the percentage of individuals with statistically significant TRA at each timepoint. Mean TRA levels may also be calculated per study group per timepoint and compared between groups.

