**Outcome measures related to estimated inhibitory concentrations:**

25. The concentration of TB31F in serum that provides >80% reduction in the average proportion of infected mosquitoes as measured in DSF after TB31F administration
26. The concentration of TB31F in serum that provides >80% reduction in the average proportion of infected mosquitoes as measured in DMFA after TB31F administration
27. The concentration of TB31F in serum that provides >80% transmission blocking activity relative to experimental controls as measured in SMFA after TB31F administration
28. The concentration of TB31F in serum that provides >80% reduction in the average mosquito infection intensity (oocyst number) as measured in DSF after TB31F administration
29. The concentration of TB31F in serum that provides >80% reduction in the average mosquito infection intensity (oocyst number) as measured in DMFA after TB31F administration
30. The concentration of TB31F in serum that provides >80% transmission reducing activity relative to experimental controls as measured in SMFA after TB31F administration

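### The exploratory DMFA/DSF IC80 and IC50 take reductions against day 0 with no day term or saline contrast, so any change in infectivity that occurs without TB31F counts toward the target

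*SAP*

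**What the plan says.** All places are in the SAP.

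- **Comparator for DMFA and DSF** (Analysis Methods, Outcome measures related to estimated inhibitory concentrations): "Baseline infection prevalence and intensity estimates will be used to calculate relative reductions in these transmission measures during follow-up". SMFA reductions are instead taken against naïve-serum control feeders.
- **Random effect in the step that estimates TRA** (same section): a negative binomial model "with random intercepts for each experiment to account for between experiments differences in oocyst intensity". No fixed effect of day is named.
- **IC80 model** (same section): the IC80 "is calculated through (mixed-effects) linear regression by regressing the square root of serum concentration on the log-mean" oocyst ratio. The printed formula is IC80 = ((log(100/(100−80)) − b0)/b1)², where b0 and b1 are the coefficients "for the intercept and slope of the linear model respectively". The IC50 is obtained in the same way.
- **Only further term offered** (same section): "To compare assays (SMFA/DMFA/DSF) we can include a categorical variable in the model as an interaction variable to allow different slopes".
- **Target** (Outcome Definitions, outcome 29): the serum concentration of TB31F that "provides >80% reduction in the average mosquito infection intensity (oocyst number) as measured in DMFA after TB31F administration". Outcome 28 is the DSF counterpart. Outcomes 25 and 26 ask the same for the proportion of infected mosquitoes.
- **Feeding days** (Outcome Definitions): DMFA on days 0, 1, 5 and 14; DSF on days 0, 1 and 5.
- **Controls** (Study design, Table 3): 15 + 15 = 30 saline participants in Cohort 2.
- **Status** (Objectives, Cohort 2): both IC80 objectives are exploratory.

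**The concern.** A reduction measured against a participant's own day 0 contains the effect of TB31F and whatever infectivity would have done without it. The printed formula deducts the whole intercept from log 5, so change at zero concentration is counted toward the 80%.

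The SAP does not say whether saline feeds enter the fit, and neither reading removes the problem. If they enter at concentration 0, b0 estimates the average natural change and is still credited to TB31F. If only recipients are fitted, b0 is an extrapolation, and change over time is mixed with the rise and fall of concentration. A random intercept per experiment does not absorb a systematic day effect.

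Elsewhere the SAP does allow for time: its models for within-individual reduction in the proportion infected and in oocyst density both include day of follow-up. Only the concentration-response model leaves out both day and the saline arm.

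At stake is the concentration reported as giving 80% or 50% reduction in DMFA and DSF. The optional comparison of IC80 between assays is also affected, because it would set values with a day-0 reference (DMFA, DSF) beside values with a same-experiment reference (SMFA).

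**Working it through.** The SAP states no IC80 value, so there is no figure to reproduce. The check is of the formula.

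**1. What the formula solves.** The wording names √C as the variable regressed, but the printed formula only follows if the log ratio is the response: log(mean oocysts day 0 / mean oocysts day t) = b0 + b1·√C. Setting the right side to log 5 = 1.609 and solving for C returns the SAP formula exactly. It is therefore the concentration at which the total reduction from day 0, intercept included, is 80%.

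**2. What TB31F alone contributes.** If the response is linear in √C, the TB31F-attributable value solves b1·√C = log 5. The ratio of the two does not depend on b1:

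reported / attributable = ((log 5 − b0)/log 5)², with b0 = −log(1 − f),

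where f is the natural fall from day 0 (negative for a rise). For the IC50, log 2 = 0.693 replaces log 5. At the reported IC80 the reduction due to TB31F alone is 1 − 0.2/(1 − f).

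**3. Numbers.** f is assumed and constant over days. For f = 20%: b0 = 0.223, (1.609 − 0.223)/1.609 = 0.861, and 0.861² = 0.74.

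| Natural change (assumed) | b0 | IC80 ratio | TB31F's own reduction at reported IC80 | IC50 ratio |
|---|---|---|---|---|
| none | 0 | 1.00 | 80% | 1.00 |
| 10% fall | 0.105 | 0.87 | 78% | 0.72 |
| 20% fall | 0.223 | 0.74 | 75% | 0.46 |
| 30% fall | 0.357 | 0.61 | 71% | 0.24 |
| 20% rise | −0.182 | 1.24 | 83% | 1.60 |

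**4. Change that builds up over days.** Simulation with 30 participants per dose arm, with or without 30 saline participants, feeds on days 1, 5 and 14, a response linear in √C, and assumed concentration-time shapes. The formula as written gave 0.82–0.85 times the true IC80 when infectivity fell naturally by 24% by day 14, 0.54–0.67 for a 50% fall, 1.16–1.19 for a 32% rise, and 1.00 with no change. With days 1 and 5 only, as for DSF, and natural falls of 5% and 20%, the median was 3.3–3.4 against a true 4.0. The direction is the same with and without saline in the fit.

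**5. Which correction holds up.** Three estimators were compared with saline included and a true IC80 of 4.0. The table shows the case of no natural change.

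| True shape of log ratio | SAP formula | Day factor, (log 5/b1)² |
|---|---|---|
| linear in √C | 4.0 | 4.0 |
| linear in C | 2.6 | 1.7 |
| proportional to C^0.3 | 4.8 | 5.5 |

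Forcing the curve through zero is therefore right only if the response is exactly linear in √C. The third estimator references reductions to same-day saline and keeps an intercept for recipients. It gave about 3.6 to 4.2 across all shapes, with and without natural change.

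**The case against.** The strongest points on the other side, and what stands of each:

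- **The bias is conditional.** This stands. The SAP gives no natural time course, so existence, sign and size are all assumed. A reader might infer that the IC80 is certainly biased downward; the document does not support that.
- **The IC80 is exploratory.** This stands. The SAP's Purpose section directs the plan at primary and secondary outcomes and leaves later exploratory work unbound by it. That limits the weight of the point. It does not make the printed formula answer the stated outcome.
- **The formula is for TRA only.** This stands. The intercept argument is shown for outcomes 28 and 29. For outcomes 25 and 26 no formula is printed, and the concern rests on the shared day-0 comparator.
- **The cited methods may hold further terms.** Possible, since the SAP says its models are similar to published ones. But the SAP prints an explicit formula, and that formula counts the intercept.
- **Spread to duration and dosing.** A reader might infer that the bias passes into the modelled duration of activity and the simulated regimens. The SAP assigns those to a separate non-linear PK/PD model, with time among its listed elements, and does not say that b0 or this IC80 enters it.
- **False-positive findings.** A reader might also infer inflated error in a test of b1 > 0. The SAP plans an IC80 with a delta-method interval and no such test.

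**Conclusion.** The point holds in conditional form. As written, the DMFA/DSF IC80 and IC50 credit TB31F with any change in infectivity since day 0 that would have occurred without it. Under an assumed constant natural fall of 10% to 30%, the reported IC80 is 0.87 to 0.61 times the TB31F-attributable value; under a 20% rise it is 1.24 times. The IC50 is more sensitive. These ratios assume a response linear in √C; with no natural change they equal 1.

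The primary day-5 DMFA analysis does not use this model and is not affected. SMFA has its own same-experiment controls, so this source of bias does not arise there, but the optional comparison of IC80 between assays would then mix two references.

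The reference should change. The finding does not justify dropping the intercept: a reader might conclude that IC80 = (log 5/b1)² is the cure, but that estimator can do worse than the SAP's when the response is not linear in √C.

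**What to change.** For DMFA and DSF, amend the concentration-response section of the SAP as follows:

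1. Express TRA and TBA in the fit relative to the change from day 0 in the concurrent saline participants on the same day (DMFA days 1, 5, 14; DSF days 1, 5). One way is to include the 30 saline participants, with day as a factor by assay.
2. Define IC80 and IC50 as the concentration giving 80% and 50% reduction relative to same-day saline.
3. Keep a free intercept for TB31F recipients. With a = that intercept net of same-day saline, IC80 = ((log 5 − a)/b1)², and log 2 replaces log 5 for the IC50. Here a describes the shape of the TB31F curve and no longer contains natural change.
4. State in any between-assay comparison which reference each IC80 uses.

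Cost: SAP wording and a few parameters. For DMFA, three day terms, a and b1 make 5 against 2 now; for DSF, two day terms, a and b1 make 4 against 2. The saline feeds are already planned, so no new data are needed. The interval will be slightly wider, and the IC80 may be less favourable.

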#### **Efficacy outcome measures related to transmission reducing activity (reductions in oocyst intensity):**

We will determine averaged within-individual percent reduction in the density of oocysts at days post-treatment (1, 5, 14) compared to baseline (day 0) for each group. This will be assessed through DMFA, DSF and SMFA and outcomes for these different feeding assays will be presented separately as percentage reduction (with 100% as total reduction of transmission, and negative values as enhanced transmission) with 95% confidence interval. For DMFA and DSF, these data will be analysed for all individuals who received the product per protocol without restrictions to baseline infectivity, and for those individuals who are infectious at baseline (i.e. infecting at least one mosquito with any number of oocysts). For SMFA, these data will be analysed for all individuals who received the product per protocol without restrictions to baseline infectivity in DMFA or DSF, as well as for the subset of individuals who are infectious at baseline. SMFA, an exploratory outcome, will be conducted after unblinding to allow testing of a realistic sub selection of test and control samples. Participants may have naturally acquired TRA due to exposure to gametocytes prior to enrollment; SMFA on baseline samples will allow us to identify these individuals. Additional samples that are most informative for determining the IC80 will be selected based on the ELISA data and tested in the SMFA. For this, one person not involved in data analysis will be unblinded and select samples based on ELISA values and treatment arm.

All analyses on within-individual percentage reduction in oocyst density will use a mixed effects negative binomial regression model with day of follow-up and dose of TB31F as fixed effects. A random intercept will be added to models to allow for participant-level variations (i.e. intra-cluster correlation).

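### The model for individual SMFA activity has no feeder-level variance, so each participant's TRA and TBA interval is too narrow if feeders differ, by an amount the SAP does not allow one to fix

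*SAP*

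**What the plan says.** The SAP section on estimated inhibitory concentrations defines SMFA TRA as the "relative reduction in oocyst intensity for test samples (one feeder per test sample") "compared to pooled naïve serum controls (two feeders"). Replication is limited: "Samples may be tested in one or two independent SMFA experiments".

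The estimate is made at the level of the single sample: "TRA values for each participant and time-point will be estimated using mixed effect negative binomial regression models". The only random effect named is "random intercepts for each experiment to account for between experiments differences in oocyst intensity". The TBA model is logistic with the same random structure. No feeder term appears anywhere in the SAP.

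Two uses at participant level follow. The same section says that the plan may report "the percentage of individuals with statistically significant TRA at each timepoint". The section on transmission reducing activity says, of people with naturally acquired activity, that "SMFA on baseline samples will allow us to identify these individuals".

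**The concern.** Within one SMFA experiment, a test serum and its feeder are the same unit. A feeder that happens to run low or high moves all of its mosquitoes together, and nothing in the data from that run separates this shift from an effect of the serum. An intercept per experiment removes differences between runs, not differences between feeders within a run. The standard error of an individual TRA or TBA then holds mosquito-level variation only.

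The SAP accepts the principle elsewhere: its DMFA and DSF models carry a participant intercept because mosquitoes fed on the same person are correlated. The SMFA model has no counterpart for mosquitoes fed from the same feeder. At stake are the individual SMFA intervals and any count of individuals whose TRA is called significant.

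**Working it through.** **Inputs from the SAP.** One test feeder; two control feeders; one or two experiments; random intercept for experiment only; significance level 0.05, taken as two-sided because the section on confidence intervals and P values does not state sidedness.

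**Inputs assumed, because the SAP gives none.** Mosquitoes per SMFA feeder m = 20 or 40; control mean mu = 20 oocysts; negative binomial k = 0.8 to 3; feeder SD s on the log scale = 0.05 to 0.3. The SAP states no error rate for this test, so there is no figure of its own to reproduce. Its power figures concern DMFA and skin feeding.

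**Formulae for an inactive serum.**
- Per-mosquito variance of the log mean: v = 1/mu + 1/k.
- Variance of the log oocyst ratio under the SAP's model: v/m for the test feeder plus v/(2m) for the controls, that is 1.5·v/m.
- True variance: 1.5·(v/m + s²).
- Ratio of true to model variance: r = 1 + m·s²/v.
- True two-sided error: 2·(1 − Φ(1.96/√r)).

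**Example.** With m = 20, mu = 20, k = 2: v = 0.05 + 0.50 = 0.55. At s = 0.2, r = 1 + 20 × 0.04/0.55 = 2.45, 1.96/√2.45 = 1.25, and the error is 21%.

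**Results over the assumed grid.** The lowest error is at m = 20, k = 0.8 (v = 1.30), the highest at m = 40, k = 3 (v = 0.383).

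| Feeder log-SD | Lowest r | Lowest error | Highest r | Highest error |
|---|---|---|---|---|
| 0.05 | 1.04 | 5.4% | 1.26 | 8.1% |
| 0.1 | 1.15 | 6.8% | 2.04 | 17.0% |
| 0.2 | 1.62 | 12.3% | 5.17 | 38.9% |
| 0.3 | 2.38 | 20.4% | 10.39 | 54.3% |

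**Check by simulation.** For the example's m, mu and k, with 10 inactive samples per experiment and 300 runs, the two-sided error was 5.6% at s = 0, then 10.6%, 21.6% and 35.0% at s = 0.1, 0.2 and 0.3. The formula gives 9.3%, 21.1% and 34.3% for the last three. The activity side alone was 5.4%, 12.3% and 20.5%, against 2.5% nominal. The other errors appear as enhanced transmission.

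**Second experiment.** Testing a sample twice halves both the model variance and the true variance. The ratio r, and so the error rate, stays the same.

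**Cut-offs for natural immunity.** The SAP's strata use TRA>50% and TRA>80%, which are thresholds on the point estimate. An inactive sample passes 50% with probability Φ(−ln 2/√(1.5·(v/m + s²))). With m = 20, k = 0.8 to 3 and an assumed 90 inactive samples, this gives about 1-4 samples at s = 0.2 and 4-7 at s = 0.3. At k = 0.8 about 1 sample passes even at s = 0. Fewer than 0.1 samples are expected above 80% at any of these SDs.

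**The case against.** **The size is not in the documents.** Feeder SD, mosquitoes per feeder, control mean and k are all assumed. At a feeder SD of 0.05 the error is close to nominal. A reader might infer that far too many participants will be called active. The SAP does not support that as a fact: it would need a feeder SD of roughly 0.2 or more, and about half of the false calls would be of enhancement. This stands.

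**Natural immunity.** A reader might also multiply the activity-side error by 90 baseline samples: with 20 mosquitoes per feeder and SD 0.2-0.3, half of 12.3% to 41.1% gives about 6 to 18 people wrongly labelled as naturally immune. The documents do not support this either. The strata rest on point cut-offs, and the sentence on identifying such people names no significance test. A correct test would itself flag 90 × 2.5%, or about 2. The SAP also says that only a selection of samples will be tested by SMFA. This objection stands too.

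**Low priority of the output.** The significance count is optional, and the section on transmission reducing activity calls SMFA exploratory. The primary efficacy endpoint is DMFA. Group means average feeder noise over many samples, and in the IC80 regression it acts mainly as residual error. This limits the reach of the point but does not remove it: SMFA TRA is also listed among the secondary efficacy objectives of Cohort 2, and the individual intervals are wrong wherever they are shown.

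**Imprecision is acknowledged.** The SAP says that low TRA estimates are imprecise and allows values inferred from antibody concentration. That does not correct the standard error of a single sample. TB31F concentration also cannot supply natural activity at baseline, before any TB31F is given.

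**Conclusion.** The point holds for the individual SMFA estimates. As specified, the model leaves out a source of variance that is fully confounded with the serum. Any feeder variance above zero makes each individual TRA and TBA interval too narrow and the optional significance count too high in both directions. Neither a second experiment under the same model nor the SAP's remarks on imprecision corrects this.

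The excess runs from negligible to several times the nominal 5%, as tabulated, and only a measured feeder SD can place it. The error rates were derived for TRA; for TBA the fault is the same, but its size was not computed. The point does not show that the natural-immunity strata are badly contaminated, nor that IC80 or group-level conclusions are unsound.

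**What to change.** Add a feeder-level random intercept to the SMFA TRA and TBA models. Estimate its variance from the paired control feeders pooled over all SMFA runs, and from samples tested twice. Use it in every individual interval and significance call. If this is not done, drop the per-individual significance count.

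The change needs model code and SAP wording, and no extra feeds. A check with feeder variance taken from the control pairs of 10 assumed experiments (t with 10 df; m = 20, mu = 20, k = 2) brought the two-sided TRA error to 4.6-5.2% for every feeder SD from 0 to 0.5.

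The price is wider intervals and fewer significant individuals. In that setting the smallest TRA that reaches significance from one feeder rises from about 33% under the SAP's model to about 41%, 51% and 61% at feeder SD 0.1, 0.2 and 0.3. If feeders prove not to differ, it rises only to about 36%.

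The feeder term widens the uncertainty around a single-feeder estimate but hardly moves the estimate. It therefore does not change who passes the 50% or 80% cut-offs, and the SAP should not present it as a remedy for the strata.
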